Study Protocol: Ovarian Hyperandrogenism in Adolescent Girls and Concomitant Metabolic Changes, Oxidative Stress, Inflammation, Oral Health and Their Relation to Diet

Poznan University of Physical Education
Dietetic Department
[name]
Principal Investigator: [name]
Phone: ([contact]

Poznan University of Medical Sciences
Department of Paediatric Dentistry
[name]
Principal Investigators: [name],
Phone: ([contact]
Department of Perinatology and Gynecology
Division of Developmental Gynecology and Sexology
Principal Investigator: [name]

STUDY PROTOCOL

Ovarian Hyperandrogenism in Adolescent Girls and Concomitant Metabolic Changes, Oxidative Stress, Inflammation, Oral Health and Their Relation to Diet

1. Introduction

Hyperandrogenism in women is a state of increased androgen production, manifested by irregular menstrual cycles, a more frequent incidence of infertility, metabolic syndrome, oxidative stress, and inflammation, as well as acne and hirsutism. In addition to ovulation disorders and the multifollicular ovaries structure in an ultrasound examination, hyperandrogenism is a typical clinical feature of the Polycystic Ovary Syndrome (PCOS), which is diagnosed in approximately 8.6% of adolescent girls. Excessive body weight makes it difficult to diagnose at an early stage of the disease and intensifies metabolic and hormonal disorders, as well as those related to oxidative stress and inflammation of the body. Some research studies suggest that PCOS may negatively affect oral health of women, increasing the risk of periodontal problems.

The main purpose of this research was to check whether serum androgen levels and concomitant metabolic changes, oxidative stress, inflammation and oral health in adolescent girls with hyperandrogenism may be related to diet.

The investigators aimed to identify the factors that increase the risk of being overweight and of obesity among adolescents with clinical features of PCOS, related to diet and DEA (Disordered Eating Attitudes).

The objective was also to investigate the relationships between markers of oxidation and markers of Systemic Inflammation and macronutrients intake, such as carbohydrates and fiber, protein (animal, plant), fats and cholesterol in normal and overweight/obese girls with clinical features of PCOS.

Additionally, the investigators would like to evaluate the relation between oral health of girls with PCOS (including condition of periodontium and dental caries) and their dietary habits, hormonal, metabolic and oxidative and inflammatory status.

2. Characteristics of tested population

The research will be carried out with the participation of 200 Caucasian adolescent girls, patients at the Gynecology and Obstetrics Hospital of Poznan University of Medical Sciences and Department of Perinatology and Gynecology, Division of Developmental Gynecology and Sexology, Poznan University of Medical Sciences, aged 13–18 years

Inclusion Criteria:

- Gender: Female
- Minimum Age: 13 Years
- Maximum Age: 18 Years
- Written consent for inclusion (girls and their parents)
- clinical and/or biochemical hyperandrogenism (hirsutism with moderate to severe acne, and/or elevation of serum total testosterone or free testosterone,
- oligoovulation (based on oligomenorrhea defined as bleeding episodes occurring less than 8 times per year or secondary amenorrhea),
- polycystic ovarian picture in an ultrasound examination (at least 12 follicles in each ovary each measuring 2-9 mm in diameter and/or ovarian volume >10 mL).

Exclusion Criteria:

- any systemic disease, thyroid dysfunction, diabetes, congenital adrenal hyperplasia, Cushing syndrome, hyperprolactinemia suggestive of pituitary adenoma and androgen-secreting tumors
- medications of continuous use,
- the use of hormonal therapy or antibiotics in the past three months,
- vitamin or supplements use,
- alcohol consumption
- smoking

3. Methods

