3.1. Evaluation of anthropometric indices and body composition

3.1.1. Anthropometric Assessment

Body mass index BMI: derived from measured body height (m) and body weight (kg) as body weight / height². Weight will be measured to the nearest 0.1 kg using digital medical scales. Height will be measured with a stadiometer attached to the scales.

Diagnosis and classification of overweight and obesity will base on BMI, according to World Health Organisation (WHO) for children aged 5–19 years overweight and obesity correspond to BMI-for-age greater than 1 standard deviation and 2 standard deviations above the WHO growth reference median, respectively.

Waist circumference (WC) will be measured to the nearest 0.1 mm using Gulick anthropometric tape between the lower border of rib margin and the upper border of iliac crest (WC-mid).

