3.10. Statistical analysis

The analyses will be performed in the PQStat v1.8.0 program and the Statistica software version 12 (StatSoft. Inc. 2014, Tulsa, USA) with significance taken as $p < 0.05$. Descriptive statistics of groups will be presented as mean and standard deviation, median and quartiles, as well as numbers and percentages, depending on the data type. The normal distribution of the data will be verified using the Shapiro–Wilk test, and the comparison of the variance of variables between the groups will be performed using the Fisher–Snedecor test. Quantitative data describing two independent groups and meeting the normal distribution will be compared using the Student’s t-test or the Student’s t-test with the Cochran–Cox correction, when the variances of the groups being compared are significantly different. The Mann–Whitney test will be used when the assumption of normal distribution is not met. The dichotomous data will be compared with the chi-square test or the Fisher’s exact test when the Cochran conditions for using the chi-square test is not met. For the ordered category data, the Cochran–Armitage trend test will be used. Pearson correlation coefficient (for normally distributed variables) and Spearman’s rank correlation (when the assumption of normality is not met) will be calculated to evaluate association between two quantitative variables.

Logistic regression (univariate and multivariate) will be carried out to identify the independent predictors of dichotomous outcomes. A multiple linear regression analysis model will be built to explain the selected dependent quantitative variables.

5. Selected literature references:

2. The Rotterdam ESHRE/ASRM-Sponsored PCOS Consensus Workshop Group. Revised 2003 consensus on diagnostic criteria and long-term health risks related to polycystic ovary syndrome (PCOS) The Rotterdam ESHRE/ASRM-sponsored PCOS consensus workshop group. *Hum. Reprod.* 2004, 19, 41–47, doi:1093/humrep/deh098.
3. World Health Organization. Growth Reference 5-19. BMI-for-Age for Girls. 2007. Available online: https://www.who.int/growthref/bmifa_girls_5_19years_z.pdf?ua=1 (accessed on 21 July 2020).

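### Does the protocol commit to separate diet–marker analyses in normal-weight and overweight/obese girls, with no way to compare the two groups?

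*Protocol*

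**What the plan says.** The third aim in the protocol's Introduction is to study how oxidation and inflammation markers relate to macronutrient intake "in normal and overweight/obese girls with clinical features of PCOS". The main purpose, stated just before, concerns adolescent girls with hyperandrogenism as a whole and makes no split by weight. Section 2 fixes the size: "The research will be carried out with the participation of 200 Caucasian adolescent girls". Section 3.1.1 defines the weight categories: "overweight and obesity correspond to BMI-for-age greater than 1 standard deviation and 2 standard deviations above the WHO growth reference median". It does not say how many girls are expected in each.

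Section 3.10 gives the methods. Two independent groups are compared by t-tests, Mann–Whitney, chi-square or Fisher's exact tests. Pearson or Spearman coefficients, depending on normality, "will be calculated to evaluate association between two quantitative variables". Logistic regression is planned for dichotomous outcomes. For continuous outcomes, "A multiple linear regression analysis model will be built to explain the selected dependent quantitative variables". The significance level is 0.05. The section does not say whether correlations are computed per weight group or over all girls, and it lists no regression terms.

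**The concern.** The objective names two weight groups, and the method in section 3.10 closest to it is a correlation of two variables, which has no place for weight status. Put together, these suggest two lists of correlations, one per group, each coefficient judged at 0.05.

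Two things would then go wrong. Each list would rest on only part of the 200 girls, so power for a relation common to both groups would fall. And a nutrient significant in one group but not in the other would invite the claim that diet acts differently by weight, although a difference in significance is not a test of a difference. At moderate power such patterns are frequent even when the relation is identical, and with several markers and nutrients a report could contain many of them.

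**Working it through.** There are two questions: how large the problem would be if the analysis were split, and whether the protocol plans that analysis.

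**1. Size, if the analysis were split**

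Inputs from the protocol: 200 girls (section 2) and a level of 0.05 (section 3.10; two-sided assumed). The protocol states no power or expected correlation, so there is no figure of its own to reproduce. Assumptions: the same true r in both groups, from 0.10 to 0.40, and a split of 100/100, with 140/60 to show the range.

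Power of one correlation test, by Fisher's z:

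power = Φ(atanh(r)·√(n−3) − 1.96) + Φ(−atanh(r)·√(n−3) − 1.96)

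For r = 0.20, atanh(r) = 0.2027.
- n = 100: 0.2027 × √97 = 1.997, so power = Φ(0.037) ≈ 0.515.
- n = 200: 0.2027 × √197 = 2.846, so power = Φ(0.886) ≈ 0.81.

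Probability of significance in exactly one group: p₁(1−p₂) + p₂(1−p₁). At 100/100 and r = 0.20 this is 2 × 0.515 × 0.485 = 0.50.

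| Common r | Power per group, n = 100 | Power, all girls | Exactly one, 100/100 | Exactly one, 140/60 |
|---|---|---|---|---|
| 0.10 | 17% | 29% | 28% | 28% |
| 0.15 | 32% | 56% | 43% | 46% |
| 0.20 | 52% | 81% | 50% | 55% |
| 0.25 | 71% | 95% | 41% | 51% |
| 0.30 | 86% | 99% | 24% | 37% |
| 0.40 | 99% | about 100% | 3% | 11% |

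A simulation with 8,000 runs per setting agrees: 49.6% at r = 0.20 with 100/100, and 55.5% with 140/60.

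For equal groups the probability is 2p(1−p), which cannot exceed 50% and reaches it at p = 0.5. With n = 100 that power occurs at r = 0.196. An assumed r of 0.20 therefore sits almost exactly at the peak. The probability is 45% or more only for r of about 0.16 to 0.235 (100/100) or 0.15 to 0.27 (140/60).

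**2. Whether the protocol plans this**

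- *Separate analyses.* Section 3.10 describes correlations between two quantitative variables and mentions no strata. The only support for a split is the objective's phrase, which can equally describe a study population covering both weight groups.
- *Main-effect regression only.* The sentence on multiple linear regression names no terms. It does not restrict the model to main effects, and a nutrient-by-weight product would fit within it.
- *Significance in one group read as a difference.* The objective is to investigate relationships. It does not say they are expected to differ, and no decision rule compares p-values between groups.
- *The two-group tests.* These do not imply stratified correlations. The second aim, on factors that raise the risk of overweight and obesity, gives them and the logistic regression a use of their own.

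**3. The usual alternative**

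A direct test of the difference in correlations at 100/100 has standard error √(1/97 + 1/97) = 0.1436 on the z scale. For r = 0.2 against 0, power is Φ(0.2027/0.1436 − 1.96) = Φ(−0.548) ≈ 29%. For 0.3 against 0 it is 58%, and for 0.4 against 0 it is 84%. The test holds its 5% level (4.8% to 5.2% in the simulation), but with 200 girls it would miss most moderate differences. A rule that pools the groups whenever this test is not significant would therefore be open to debate too.

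**The case for a change.** The strongest case for the concern is that this objective, unlike the others on relations with diet, names the two weight groups, and the Introduction says that excess weight intensifies oxidative stress and inflammation. A reader may fairly infer that the relation is to be seen in each group. Section 3.10 names no method for comparing relations. The multiplicity is real as well: section 3.2 lists six serum markers and the objective about six intakes, giving 36 pairs. At 100/100 with identical relations, one-group-only results would number about 36 × 0.278 = 10 at r = 0.10 and 36 × 0.50 = 18 at r = 0.20. Even with no relation at all there would be 36 × 0.095 = 3.4.

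The statistical principle stands: if the relations are analysed by weight group, a difference should be claimed only from a direct comparison. What does not follow is that the protocol breaks this principle. A plausible inference about a possible analysis is not a commitment to it, and the planned regression leaves room for the comparison.

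**Conclusion.** The concern does not hold. The protocol neither prescribes stratified correlations, nor excludes an interaction term, nor claims effect modification from discordant significance. What is left open is whether estimation is pooled or stratified and which terms enter the regression. A protocol commonly leaves both to the statistical analysis plan, and that plan may exist but is not shown.

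The calculations are correct under their assumptions. At a common r of 0.20 and a 100/100 split, power is 52% per group against 81% on all girls, and one-group-only significance occurs half the time. Across r = 0.10 to 0.40 that last figure runs from 3% to 50% at 100/100, and from 11% to 55% at 140/60. None of these inputs beyond the 200 girls and the 0.05 level is in the protocol. The figures describe a risk in one possible analysis and do not show an error in the plan.

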3.1. Evaluation of anthropometric indices and body composition

3.1.1. Anthropometric Assessment

Body mass index BMI: derived from measured body height (m) and body weight (kg) as body weight / height². Weight will be measured to the nearest 0.1 kg using digital medical scales. Height will be measured with a stadiometer attached to the scales.

Diagnosis and classification of overweight and obesity will base on BMI, according to World Health Organisation (WHO) for children aged 5–19 years overweight and obesity correspond to BMI-for-age greater than 1 standard deviation and 2 standard deviations above the WHO growth reference median, respectively.

Waist circumference (WC) will be measured to the nearest 0.1 mm using Gulick anthropometric tape between the lower border of rib margin and the upper border of iliac crest (WC-mid).

3.1.2. Body Composition Assessment

All measurements will be conducted after a 12 h fast. Body composition will be assessed with a Tanita MC 780 body composition analyzer, which uses bioelectrical impedance analysis (BIA method). In this model, the accuracy of measurement for the individual components, including adipose tissue, is 100 g. The measurements of fat mass (FM) will be expressed as a percentage (%) and kilograms (kg).

3.2. Biochemical parameters

Blood samplings performed in the early follicular phase (days 3–5).

Hormonal and biochemical parameters, including follicle-stimulating hormone (FSH), luteinizing hormone (LH), total testosterone, androstendione, estradiol, dehydroepiandrosterone (DHEA-S), Sex Hormone Binding Globulin (SHBG), fasting glucose and fasting insulin, total cholesterol (TC), high-density lipoprotein cholesterol (HDL-C), and triglycerides (TG), 17 OH-Progesterone, Prolactin, Cortisol, Thyroid-stimulating hormone (TSH), will be measured in the morning after overnight fasting.

Study Protocol: Ovarian Hyperandrogenism in Adolescent Girls and Concomitant Metabolic Changes, Oxidative Stress, Inflammation, Oral Health and Their Relation to Diet

Biochemical analyses will be performed in the central hospital laboratory of the Gynecology and Obstetrics Hospital of Poznan University of Medical Sciences.

Serum concentrations of the inflammation markers: Interleukin 1 (IL-1), Interleukin 6 (IL-6), Tumor Necrosis Factor (TNF- α), C-reactive protein (CRP) and the markers of oxidation: malondialdehyde, total antioxidant capacity will be measured with a commercial ELISA assay kits in the Department of Clinical Biochemistry and Laboratory Medicine, Poznan University of Medical Sciences .

3.3. Saliva assays

Samples of unstimulated saliva will be taken with a use of a saliva cotton roll commercial collection device at the dental office (University Center of Stomatology and Specialist Medicine). Biochemical analysis of the salivary TNF- α , IL-6, IL-1 β , and testosterone will be carried out with the use of commercial ELISA assay kits.

3.4. Dental examinations

The state of oral hygiene will be evaluated according to the Silness-Löe plaque index (PI) on the six index teeth: 16, 12, 24, 36, 32, 44. The gingival health will be assessed with the use of the Gingival Index (GI) by Löe and Silness on the same index teeth. The probing depth (PD) measurements will be done using a Williams manual periodontal probe. Bleeding upon probing score (BOP%) will be assessed as the proportion of bleeding sites when stimulated by a periodontal probe (the measurements recorded on all teeth present). Dental caries experience will be presented as a number of teeth with decay (D), missing due to decay (M), and filled due to decay (F) (DMT index).

3.5. Assessment of subgingival microflora

Samples of dental plaque will be collected from each patient by inserting paper points into buccal sites of gingival sulci. A real-time PCR method for the identification of 9 subgingival microorganisms: *Aggregatibacter actinomycetemcomitans*, *Porphyromonas gingivalis*, *Tannerella forsythia*, *Treponema denticola*, *Fusobacterium nucleatum*, *Prevotella intermedia*, *Peptostreptococcus micros*, *Eubacterium nodatum*, and *Capnocytophaga gingivalis*, as well as total subgingival bacterial count.

3.6. Nutrition Evaluation

Nutrition evaluation will be conducted by continuous recording of all consumed foodstuffs, dishes and beverages, specifying home measures and weight (using “The Album of photographs of products and dishes”). The method used in this study to assess eating habits will be the qualitative-quantitative method of current quotation (3-day food record). Data will be analysed using The Aliant computer program (Cambridge Diagnostics).

In each case, the analyzed daily food intake will be compared with the current, individual daily nutritional and energy requirement in accordance with the Human Nutrition Standards of the Food and Nutrition Institute, taking into account the availability of energy at the level recommended for girls.

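### Three recorded days stand in for habitual diet, so day-to-day variation weakens simple diet–marker correlations, can bias multivariable coefficients either way, and misclassifies girls against requirements

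*Protocol*

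**What the plan says.** Section 3.6 of the protocol fixes the dietary instrument and what it is taken to measure: "The method used in this study to assess eating habits will be the qualitative-quantitative method of current quotation (3-day food record". It then fixes a use at the level of the single girl: "In each case, the analyzed daily food intake will be compared with the current, individual daily nutritional and energy requirement". It does not say which days are recorded, whether they include a weekend day, or how the three days are combined.

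The Introduction makes diet an explanatory factor for androgens, metabolic changes, oxidative stress, inflammation and oral health. One objective names "relationships between markers of oxidation and markers of Systemic Inflammation and macronutrients intake", and the nutrients are listed as "macronutrients intake, such as carbohydrates and fiber, protein (animal, plant), fats and cholesterol in normal and overweight/obese girls". Another relates oral health to dietary habits.

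Section 3.10 provides Pearson or Spearman coefficients, which "will be calculated to evaluate association between two quantitative variables", and logistic regression, and adds: "A multiple linear regression analysis model will be built to explain the selected dependent quantitative variables". No usual-intake or measurement-error adjustment is mentioned. On size, section 2 says "The research will be carried out with the participation of 200 Caucasian adolescent girls".

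**The concern.** The questions are about how a girl usually eats, but the observation is three days. What she ate on those days is her usual intake plus random variation from day to day. Section 3.6 treats the two as the same thing, both as the diet variable and in the comparison with her requirement.

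Three consequences follow if the protocol is carried out as written:

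- A simple correlation between a nutrient and a marker is attenuated. The factor depends on how much that nutrient varies from day to day, so a more variable nutrient can look less related to inflammation or oxidation for purely technical reasons.
- In a model with several correlated nutrients, error in one leaks into the coefficients of the others, which can move up or down.
- A girl can be placed on the wrong side of her requirement, and any group share built from such comparisons is distorted.

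**Working it through.** **Inputs.** Three days (section 3.6); n = 200 (section 2); significance level 0.05 (section 3.10; two-sided assumed). The protocol states no power, expected correlation, variance ratio or prevalence, so there is no figure of its own to reproduce.

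**Assumptions.** Each recorded day is usual intake plus independent random error; the three days are averaged; usual intake is roughly normal. Let λ be the within- to between-girl variance ratio, assumed to lie between 1 and 4.

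**Simple correlation.** Observed r = true r × a, with a = 1/√(1 + λ/3). For λ = 1, a = 1/√1.333 = 0.87. For λ = 4, a = 1/√2.333 = 0.65.

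**Power.** Φ(atanh(r) × √197 − 1.96). An illustrative true r of 0.25, measured without error, gives 95%.

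**Share below a one-sided requirement.** Observed share = Φ(z × a), where Φ(z) is the true share.

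**Individual classification.** Take a requirement 1 SD below the mean usual intake. Among girls recorded below it, the fraction truly below is Φ₂(−1, −a; a)/Φ(−a), where Φ₂ is the bivariate normal probability with correlation a.

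| λ | a | true r 0.25 seen as | power | true 10% seen as | true 50% seen as | true 80% seen as | flagged girls truly below |
|---|---|---|---|---|---|---|---|
| 1 | 0.87 | 0.22 | 87% | 13% | 50% | 77% | 62.5% |
| 2 | 0.77 | 0.19 | 79% | 16% | 50% | 74% | 51% |
| 3 | 0.71 | 0.18 | 71% | 18% | 50% | 72% | 45% |
| 4 | 0.65 | 0.16 | 64% | 20% | 50% | 71% | 41% |

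For an acceptable range with two limits, direction again depends on where the group lies. At λ = 3, with the range at ±1 SD around the mean, a true 32% outside is seen as 48%. With the range at +1 to +3 SD, a true 84% outside is seen as 78%.

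**Multivariable model.** Observed coefficients are (S + E)⁻¹Sβ, where S is the correlation matrix of usual intakes and E holds the error variances. Take two nutrients correlated 0.7, with λ = 1 and 3. Then S + E has diagonal 1.333 and 2.000 and off-diagonal 0.7; its determinant is 1.333 × 2 − 0.49 = 2.177.

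- True β = (0, 1), so Sβ = (0.7, 1). First coefficient: (2 × 0.7 − 0.7 × 1)/2.177 = 0.32. Second: (1.333 × 1 − 0.7 × 0.7)/2.177 = 0.39. The null nutrient acquires an effect, and the real one loses more than half.
- True β = (0.30, 0.30), so Sβ = (0.51, 0.51). First: (2 − 0.7) × 0.51/2.177 = 0.305. Second: (1.333 − 0.7) × 0.51/2.177 = 0.148. Two equal effects look unequal.

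**The case against.** The size rests entirely on an assumed variance ratio. At λ = 1 the effect is mild, and no figure in the protocol is contradicted. That stands, and it is why only a range is given.

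De-attenuation and usual-intake methods are commonly left to a statistical analysis plan, which may exist but is not shown. That stands too, so the missing formula is not the complaint. The instrument, the equation of three days with habits, the girl-by-girl comparison and the unspecified days are fixed, or left open, in the protocol itself. Which days are recorded is a matter of data collection that no later analysis can repair.

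Several stronger readings are tempting, but the documents do not support them.

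- A reader might infer that every diet association shrinks toward zero. That holds for simple correlations under this error model, not for the multiple regression in section 3.10.
- A reader might infer that the share of girls outside requirements is always overstated. It is overstated below half, unchanged at half and understated above half. Nor does the protocol commit to reporting such a share. If only mean intake relative to requirement is reported, random day variation does not bias that mean.
- The 3-day mean is an inference, because section 3.6 speaks only of daily intake. If single days were compared, the error would be larger: 1/√(1 + λ) gives a factor of 0.71 to 0.45.
- Nothing says that daily values are discarded, or that a ranking of nutrients is planned.

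**Conclusion.** The point holds as a cheap improvement to the plan, not as an error that invalidates it. A 3-day record is a legitimate instrument and need not be replaced. Used unadjusted as a measure of habits, and with λ from 1 to 4, it multiplies simple correlations by about 0.87 to 0.65, unequally across nutrients. Regression coefficients for correlated nutrients can be wrong in either direction. With a cut-off at −1 SD, only 62.5% to 41% of girls flagged as below requirement truly are. Any reported share below a one-sided requirement moves toward 50%.

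These figures assume random, independent day-to-day error, averaging of three days and approximate normality. They do not cover systematic misreporting. The power loss (95% to between 87% and 64% for a true r of 0.25) describes what the short window costs. A reader might infer that correction would restore it, but it would not.

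**What to change.** 1. In section 3.6, describe the measure as recorded intake over three days. State how the days are combined, require a weekend day and, where feasible, make the days non-consecutive.
2. Keep the three daily values in the analysis file and estimate within-girl variance for each nutrient. With 200 complete records this has 200 × 2 = 400 degrees of freedom.
3. As a secondary analysis, report de-attenuated correlations (observed r × √(1 + λ̂/3)) or regression-calibrated slopes, with intervals, beside the raw ones. Where several nutrients enter one model, calibrate them jointly. Where normality fails, apply the correction after a suitable transformation rather than to a Spearman coefficient directly.
4. If a share below requirement is reported, base it on the variance-adjusted distribution of usual intake. Present the girl-by-girl comparison as describing the recorded days only.
5. Do not compare nutrients on raw correlations alone.

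Cost: a modest extra analysis of data already collected, plus an instruction on the choice of days. Corrected estimates have wider intervals, and significance tests and power are essentially unchanged. If the days are consecutive, within-girl variance may be understated and the correction too small.
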